7.7 Safety Hypotheses

Safety is assessed by the rate of anticipated complications due to treatment. The primary complications expected are strictures, bleeding, and esophageal perforation). It is hypothesized that the complication rate in the EndoRotor arm will be no greater than in the control arm.

$$\begin{aligned} \text{Null Hypothesis: } & \text{Erate} > \text{Crate} \\ \text{Alternate Hypothesis: } & \text{Erate} < \text{Crate} \end{aligned}$$

Where:

Erate = Rate of Bleeding, Perforation and Stricture for EndoRotor

Crate = Rate of Bleeding, Perforation and Stricture for Control

Testing will be completed using Fisher's Exact test with two-tailed $\alpha = 0.05$

Further, subsets of complications assessed to be serious (e.g., serious adverse events) will be compared, as appropriate.

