4.2 Overview of Study Design

This is a prospective, multi-center, randomized study to compare the safety and performance of the EndoRotor® Mucosal Resection System with continued ablative therapy in subjects with refractory dysplastic Barrett's Esophagus. Subjects must have failed 3 RFA treatments (failure of Barrett's to respond to RFA with a decrease of at least 50% of its length) and following 3 RFA failures have no endoscopic and histologic evidence of esophageal adenocarcinoma at the time of therapy. The subjects are randomized and treated (up to 2 times) with either the EndoRotor® which resects the affected mucosa and submucosa (down to the muscularis propria layer), or with cryotherapy or ablative therapy of the persistent lesions. Subjects will be followed with biopsies of the resected areas at the time of surveillance endoscopies every 3 months until they have 2 consecutive negative endoscopies and biopsies (6 months). Those who are positive after 2 treatments will exit the study and will be deemed treatment failures.

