5.6 Follow-Up Procedures and Therapy Transitions

Surveillance endoscopy is performed in 3 months where there is visual inspection of the treated areas. Biopsies are taken from the areas treated with the respective device are sent to pathology to evaluate for the presence of intestinal metaplasia (Barrett's). If the samples are read as negative by Pathology (no Barrett's seen), the patient then undergoes another endoscopy in 3 months. If the results again are negative, the patient is declared to have a complete response to the treatment (EndoRotor® or ablative therapy).

If there is intestinal metaplasia (Barrett's) confirmed by the biopsy, the patient undergoes a second treatment with either the EndoRotor® or ablative therapy as described in Section 5.7. Two consecutive negative results at 3 month intervals between biopsies is required to consider these subjects complete responders.

If there is intestinal metaplasia (Barrett's) seen either at 90 days or at 180 days after either (EndoRotor® or cryotherapy / ablative therapy) second treatment, the patient is considered to have failed and will exit the study.

To evaluate the secondary endpoint of this study, "Percent reduction of the area with Barrett's esophagus that was resected or ablated during the initial treatment session through the final follow-up visits", percent reduction of the area with Barrett's esophagus will be determined by a decrease in overall length. Using the Prague criteria, both the circumference and maximal length of the Barrett's segment will be estimated. A percentage reduction in the length will be calculated by length measured at the follow up endoscopy divided by the total prior length.

Adverse events, as defined in Section 10.4, will be recorded from the index procedure (Day 0) through study completion and/or exit/withdrawal.

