7.2 Analysis Populations

The safety analysis population is defined as all subjects who are treated with either EndoRotor® or continued ablative therapy. Subjects will be analyzed as treated.

The primary effectiveness analysis population is intent to treat (ITT), defined as all subjects who are randomized. Subjects will be analyzed as randomized. Missing primary and secondary endpoint data will be imputed.

A supportive effectiveness analysis population is Per Protocol (PP). This population is a subset of ITT and requires that subjects be treated with either EndoRotor® or continued ablative therapy, meet all inclusion/exclusion criteria, and are evaluated for effectiveness at no fewer than two post-treatment visits 3 months apart. Subjects will be analyzed as treated. Missing data will not be imputed.

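### The complication test in Section 7.7 does not separate risk per treatment from number of treatments, which depends on response and is expected to differ between arms

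*Combined protocol and SAP*

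**What the plan says.** Section 7.7 sets the formal safety comparison. It opens: "Safety is assessed by the rate of anticipated complications due to treatment". The quantity is defined as "Erate = Rate of Bleeding, Perforation and Stricture for EndoRotor", with a matching rate for control, and "Testing will be completed using Fisher's Exact test with two-tailed" alpha of 0.05. No denominator (subject, treatment or time) and no event window is given there. Section 7.2 supplies the likely unit: "The safety analysis population is defined as all subjects who are treated with either EndoRotor® or continued ablative therapy".

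The number of treatments is set elsewhere. Section 4.2: "The subjects are randomized and treated (up to 2 times"). Section 5.6: "If there is intestinal metaplasia (Barrett's) confirmed by the biopsy, the patient undergoes a second treatment with either the EndoRotor® or ablative therapy". Adverse events, also in Section 5.6, "will be recorded from the index procedure (Day 0) through study completion and/or exit/withdrawal". Section 7.3 plans on 80% response with EndoRotor and 50% with control.

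Section 7 contains no index-treatment comparison, no per-treatment complication rate and no adjustment for the number of treatments. Section 7.8.4 promises a summary of operative characteristics and outcomes by arm, in general terms only.

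**The concern.** Each treatment is an opportunity for a complication. If one arm needs more second treatments because it clears less disease, more of its subjects will have an event even when the two procedures are equally risky. A cumulative per-subject rate then mixes two things: how risky the procedure is, and how often it had to be repeated.

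This matters because Section 7.7 frames the comparison as complications caused by treatment, and it is the only formal test behind the primary safety endpoint. A similar or lower rate on EndoRotor could be reported as evidence about the procedure when part of it reflects fewer procedures. Section 4.3.2 also compares adverse events with the literature, and that comparison is hard to read unless the unit is known.

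**Working it through.** **Inputs from the documents.** Response 80% vs 50% and 55 evaluable subjects per arm (7.3); at most two treatments (4.2); a second treatment only after a positive biopsy (5.6, and the scenarios in 5.7.1); Fisher's test, two-tailed 0.05 (7.7).

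**Assumptions.** The documents plan no complication risk per treatment. I use p = 10%, with 5% and 20% as a range, the same and independent at each treatment.

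**The plan's own figure.** No figure is given for the safety test. The effectiveness power confirms the planning inputs. With the pooled normal approximation, (0.30 − 1.96 × √(2 × 0.65 × 0.35/55)) / √((0.16 + 0.25)/55) = 1.41, which gives 92.1% power against the stated 91.6%.

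**Share treated twice.** A subject is a final failure only after a positive biopsy following a second treatment, so every final failure has had two. Let s be the share of all subjects who respond only after the second treatment. Then f = (1 − response) + s, that is 0.20 + s for EndoRotor and 0.50 + s for control if s is equal in both arms. Control has 50% responders, so s runs from 0 to 0.50.

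**Per-subject risk.** 1 − (1 − p)(1 − fp) = p[1 + f(1 − p)].

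| Case, p = 10% | f, EndoRotor vs control | Mean treatments | Per-subject rate |
|---|---|---|---|
| s = 0 | 0.20 vs 0.50 | 1.20 vs 1.50 | 11.8% vs 14.5% |
| s = 0.50 | 0.70 vs 1.00 | 1.70 vs 2.00 | 16.3% vs 19.0% |

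Control receives 25% more treatments in the first row (1.50/1.20) and 18% more in the second (2.00/1.70). The gap in per-subject rates is p(1 − p)(0.30) = 2.7 points in both, or about 1.5 subjects out of 55.

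**What equal rates would hide.** Hold control at p = 10% and solve for the EndoRotor risk that gives the same per-subject rate.
- s = 0: 1.2p − 0.2p² = 0.145 gives p = 12.3%, which is 23% higher.
- s = 0.50: 1.7p − 0.7p² = 0.190 gives p = 11.7%, which is 17% higher.

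A different assumption, the same chance of success at each session, gives f = √0.2 = 0.447 and √0.5 = 0.707, rates of 14.0% vs 16.4%, and again about 17% hidden.

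**When the direction reverses.** EndoRotor has more second treatments only if its late-responder share exceeds control's by more than 30 points of all subjects. For example, with 80% vs 50% treated twice, the rates are 17.2% vs 14.5%.

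**Effect on the test.** Exact enumeration at 55 per arm, with equal per-treatment risk and the same success chance at each session, gives these probabilities of a significant result favouring EndoRotor.

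| p | Day 0 to exit | Index treatment only |
|---|---|---|
| 5% | 1.5% | 0.4% |
| 10% | 2.8% | 1.0% |
| 20% | 4.6% | 1.4% |

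**The case against.** The strongest reply is that this is a choice of question, not an error. The trial randomises subjects to strategies of up to two treatments, the effectiveness endpoint is defined the same way, and needing fewer procedures is a real benefit to the patient. A per-subject comparison of strategies is legitimate. That stands, and it is why the cumulative comparison should stay.

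A reader might infer that the plan necessarily makes EndoRotor look safer. The documents do not support that. Exposure depends on response to the first treatment, which is not given; 80% and 50% refer to response after up to two. Arm-specific rules pull both ways. The 270-degree limit on circumferential resection (5.5.3) could leave disease to treat later, while counting only biopsies from the treated segment in the EndoRotor arm (5.8.1) could reduce re-treatment.

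A reader might also infer that failures are simply observed for longer. Section 5.7.1 does not bear this out: Scenario 2 failures leave at 6 months, as Scenario 1 responders do, and Scenario 3 responders stay 9 months. Treatment count carries the argument, not follow-up time.

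Nor does the formal test become seriously misleading. In the cases above, the chance of a false significant result favouring EndoRotor at 10% risk is 2.8%, close to the nominal 2.5% per tail. Exactly equal rates would not meet the alternative in 7.7 in any case.

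Finally, listings by CRF module (7.1) and the 7.8.4 summaries would allow a per-treatment description afterwards. They do not pre-specify one.

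**Conclusion.** The point holds in a limited form. Section 7.7 should be read as comparing subjects with an event from Day 0 to exit, although the unit is inferred from Fisher's test and Section 7.2. On that reading, its result cannot distinguish a safer procedure from fewer procedures. The planned response rates imply at least 20% vs 50% of subjects treated twice. With an equal share of late responders and 10% risk per treatment, equal per-subject rates are compatible with an EndoRotor per-treatment risk 17% to 23% higher; the upper figure requires that no subject in either arm responds late. Both figures assume equal, independent risk at each session. The sign is expected but not guaranteed, and the consequence is for the estimate and its interpretation far more than for the p-value. This is a worthwhile, inexpensive improvement, not a flaw that invalidates the safety analysis.

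**What to change.** In Section 7.7:

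1. State that the unit is the treated subject with at least one bleeding, perforation or stricture event from Day 0 to exit, and label the existing Fisher comparison as the result for the strategy of up to two treatments.
2. Pre-specify a supportive comparison of the same events from Day 0 to the first surveillance visit, ending before any second treatment. Section 5.7.2 allows treatment at that visit, so the cut-off needs to be explicit. Every treated subject then has one treatment and about three months of planned follow-up.
3. Pre-specify, by arm, the number of treatments per subject and complications per treatment, with a method that allows for two treatments in the same subject (for example a generalised estimating equation or a cluster-robust interval).
4. Base any statement about procedural safety on items 2 and 3.

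The cost is SAP wording and additional tables from data already collected; Section 10.5 requires event start dates, and Sections 5.7.2 to 5.7.4 require repeat treatments to be recorded. There are two drawbacks. The index window has fewer events and leaves out complications of second treatments, so it should supplement the cumulative comparison and not replace it. Second treatments are given to subjects selected by non-response, so the per-treatment rates are descriptive, whereas the index-window comparison keeps the randomised groups nearly intact.

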1.3 Literature Summary

Although most patients under surveillance for BE do not develop dysplastic tongues or segments, those that do require intervention to avoid progression to EAC. Historically BE patients were treated with endoscopic mucosal resection (EMR) of neoplasia and although EMR produces samples that can be histologically interpreted, a stepwise radical endoscopic resection (SRER) of the Barrett's mucosa is associated with a high stenosis rate of 48%.⁽³⁾ This directly led to the development of Radio Frequency Ablation (RFA), which utilizes balloons to deliver thermal energy circumferentially to ablating the abnormal lining using radiofrequency energy of superficial BE lesions. More recent developments have narrowed the area of treatment using focal ablation catheters. The use of RFA has shown to be effective in BE eradication typically requiring an average of three treatments with reduced stenosis rates (5%) over EMR but although it is relatively fast and easy to perform, it is expensive (over \$2,500 per procedure), it does not harvest tissue for pathological evaluation, and adverse events such as stricture (5%) and bleeding (1%) can occur.⁽⁶⁾ A majority of patients will experience chest pain after the procedure which usually lasts a few days, and in 1-2% of patients the pain is more severe and longer lasting.^(7,8) Current literature shows up to 10% of patients will continue to develop BE despite 3 separate RFA treatments at which point they are considered refractory.

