4.3.2 Primary Safety Endpoint

Assessment of Adverse Events (incidence, relationship to device and severity) compared to the control arm and the medical literature.

Adverse events will be compared to the control therapy.

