7.3 Sample Size

Assuming a response rate for Barrett's esophagus with EndoRotor® ablative therapy of 80%, and for cryoablation of 50%, the study will have over 95% power to demonstrate non-inferiority (NI), given a NI delta of 10%, of EndoRotor® to cryoablation and will have 91.6% power to demonstrate superiority of EndoRotor® over continued ablative therapy using a sample size of 110 evaluable subjects, 55 in each treatment group.

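### Section 7.7 claims a complication rate no greater than control but tests it with a two-tailed Fisher test and no margin or interval for the difference, so a non-significant result would not support the claim

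*Combined protocol and SAP*

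**What the plan says.** Section 7.7 (Safety Hypotheses) puts the claim in words: "It is hypothesized that the complication rate in the EndoRotor arm will be no greater than in the control arm". It then writes a null of Erate > Crate and an alternative of Erate < Crate. The quantity compared is a composite: "Erate = Rate of Bleeding, Perforation and Stricture for EndoRotor", and likewise for control. The method is given as: "Testing will be completed using Fisher's Exact test with two-tailed" alpha of 0.05.

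Section 4.3.2 defines the primary safety endpoint as "Assessment of Adverse Events (incidence, relationship to device and severity) compared to the control arm and the medical literature". Section 7.7 does not itself use the word primary, but it contains the only formal between-arm safety test in the plan.

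Section 7.2 sets the population: "The safety analysis population is defined as all subjects who are treated with either EndoRotor® or continued ablative therapy", analysed as treated. The power statements in Sections 4.7 and 7.3, the latter "using a sample size of 110 evaluable subjects, 55 in each treatment group", concern effectiveness only, as does the 10% margin in Sections 7.6 and 7.8. The nearest thing to an expected control complication rate is the literature summary on radiofrequency ablation in Section 1.3: "adverse events such as stricture (5%) and bleeding (1%) can occur".

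**The concern.** The claim, the hypotheses and the test are three different things. *No greater than* is a one-sided claim that includes equality and, to be provable with a finite sample, needs a margin. The written alternative is strict superiority. The two-tailed Fisher test has equality as its null and can only show that the rates differ. With uncommon complications and about 55 to 60 subjects per arm, the likely outcome over a wide range of true rates is p>0.05. That neither establishes the written alternative nor shows that the rate is no greater than control. The stake is the main comparative safety statement of a study that Section 4.5 calls pivotal: the report could carry a non-significant p-value beside the claim while a materially higher complication rate remains compatible with the data.

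**Working it through.** **1. The plan's own figure.** The only power figure stated to a decimal is for effectiveness: 91.6% for superiority, 80% vs 50%, 55 per arm (Section 7.3). With the pooled-variance normal approximation, power = Φ{[0.30 − 1.96·√(2·0.65·0.35/55)] / √[(0.80·0.20 + 0.50·0.50)/55]} = 92.1%, which agrees closely. There is no safety figure to reproduce.

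**2. Side by side with effectiveness.** Sections 7.6 and 7.8 give effectiveness a margin (10 points), a null that includes the boundary, and a decision by the lower limit of a two-tailed 95% CI for the difference. Section 7.7 has none of these for safety. The Clopper-Pearson intervals in Section 7.1 are for single proportions, tabulated by arm, and do not bound the difference.

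**3. Inputs for the operating characteristics.**
- Test: two-tailed Fisher, reject if p ≤ 0.05 (Section 7.7).
- Arm size: 55 (evaluable, Section 7.3). The safety set is all treated subjects, and 120 are enrolled 1:1 (Sections 4.5 and 5.2), so at most about 120/2 = 60 per arm.
- Control rate: not stated for the composite. Assumption: 5% + 1% = 6% (Section 1.3), then varied.

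**4. Method.** Exact enumeration: the sum over all (x, y) of Bin(x; n, pE)·Bin(y; n, pC), counting pairs with Fisher p ≤ 0.05, split by direction.

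| True EndoRotor vs control | Direction counted | n = 55 | n = 60 |
|---|---|---|---|
| 12% vs 6% (doubled) | EndoRotor higher | 10.1% | 11.8% |
| 18% vs 6% (tripled) | EndoRotor higher | 37.4% | 42.2% |
| 6% vs 6% | EndoRotor lower | 0.6% | 0.7% |
| 0% vs 6% | EndoRotor lower | 11.1% | 15.0% |

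The last row can be checked by hand. With 0 EndoRotor events, significance needs at least 6 control events (0/55 vs 5/55 gives p = 0.057; 0/55 vs 6/55 gives p = 0.027), and P(Y ≥ 6) for Bin(55, 0.06) is 0.111.

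**5. Dependence on the control rate: chance of detecting a doubling.**

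| Control rate | n = 55 | n = 60 |
|---|---|---|
| 3% | 2.6% | 3.3% |
| 6% | 10.1% | 11.8% |
| 10% | 21.9% | 24.7% |
| 15% | 38.4% | 41.8% |
| 17% | 45.5% | 49.2% |
| 18% | 49.0% | 52.9% |
| 20% | 56.0% | 60.0% |
| 30% | 84.6% | 89.4% |

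The 50% point lies at a control rate of about 18% with 55 per arm and just above 17% with 60.

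**6. What a non-significant result leaves open.** Newcombe 95% intervals for EndoRotor minus control, 55 per arm:
- 3 vs 3 events: p = 1.0, interval −10.1 to +10.1 points.
- 6 vs 3 events: p = 0.49, interval −5.6 to +16.9 points.
- 10 vs 3 events: p = 0.073. The difference is 18.2% − 5.5% = 12.7 points. The Wilson limits are 10.2% to 30.3% and 1.9% to 14.9%. Lower limit: 12.7 − √(8.0² + 9.4²) ≈ 0.4; upper limit: 12.7 + √(12.1² + 3.6²) ≈ 25.4.

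In the third case Fisher is non-significant although the interval lies wholly above zero; 11 vs 3 events would be needed for p ≤ 0.05 (p = 0.042).

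**The case against.** Several points on the other side stand.

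- A reader might infer that the test cannot support the claim at all. That goes too far. A significant result with EndoRotor lower would establish Erate < Crate, which implies no greater than control and is the alternative as written.
- A reader might also infer that p>0.05 is close to certain whatever the truth. It is not. With 55 per arm, 24% vs 6% is detected 69% of the time, and 0% vs 15% gives significance favouring EndoRotor 85% of the time.
- The 6% is soft. It adds two literature figures for radiofrequency ablation, leaves out perforation and cryotherapy, and describes patients in general rather than those with three failed ablations. Section 7.7 sets no severity threshold for bleeding; if intra-procedural bleeding counts, the rate could be much higher and the power better.
- Section 7.7 does not label its hypothesis primary, safety is outside the testing sequence in Section 7.8.3, and nowhere do the documents say that p>0.05 will be read as comparable safety. That reading is a risk, not a stated plan.
- Safety does not rest on this p-value alone: per-arm intervals (7.1), comparison of serious events (7.7) and review by a data monitoring committee with stopping rules in its charter (10.2) are also planned.
- The strict signs that leave equality in neither hypothesis may be typographical. The signs in Section 7.6 do include equality, so this cannot be settled from the text.

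None of this supplies a margin or an interval for the difference, and none makes non-significance evidence for the claim.

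**Conclusion.** The concern holds in this form: the stated test does not match the stated safety claim, and a non-significant result would not support it. That part is a matter of logic and does not depend on any assumed rate. How often the test would miss a real excess does. At an assumed 6% control rate a doubling is detected about 10% of the time with 55 per arm (12% with 60). It is missed more often than not only up to a control rate of about 17-18%; above that it is detected more often than not. Success in the favourable direction is possible but unlikely at low control rates: 11% (15%) at 6%, even if EndoRotor caused no complications at all.

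**What to change.** In Section 7.7, make the main safety comparison the EndoRotor minus control difference in the composite rate, in the safety population, with a two-sided 95% Newcombe or Miettinen-Nurminen interval. State that a Fisher p-value above 0.05 is not evidence that the rate is no greater than control. If a formal claim is wanted, replace the hypothesis pair with H0: Erate − Crate ≥ margin against H1: Erate − Crate < margin, with a margin that the sponsor pre-specifies and justifies, and judge it by the upper confidence limit.

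The change is to SAP wording and needs no new data or subjects. Its cost is candour: the interval will be wide, about −10 to +10 points at 3/55 vs 3/55. A formal margin claim may also have low power. At equal true rates of 6%, 55 per arm and one-sided 0.025, power = Φ(margin/√(2·0.06·0.94/55) − 1.96), which is 20%, 60% and 91% for purely illustrative margins of 5, 10 and 15 points. If that is too low for a margin the sponsor can defend, the comparison should stay an estimate with its interval.
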